Official Title: Supplement to Hospital to Home Outcomes (H2O): A Study to Improve the Fluidity of Transitions Between Hospital and Home

NCT: 03224130

Date: 20 September 2018

H2O Statistical Analysis Plan for Supplement (AIM 4)

Prepared by:

[name]

[name]

Date:

11/3/2016

Analysis plan approved by:

[name], MSCE

Professor, Division Director

Division of Hospital Medicine

PI H2O

The results of H2O Supplement (Aim 4) will be assessed as described in this document. This statistical analysis plan begins with an overview of the key components of the study including its design, objectives, and outcome measures. This is followed by a detailed description of the statistical analyses that will be utilized to address H2O Supplement Grant Aim 2 study hypotheses.

- 1. Overview of study: This study is single center, parallel, randomized trial to evaluate the effectiveness of a nurse phone call. Patients that meet eligibility criteria will be randomized 1:1 to receive either the intervention group (a nurse phone call within 96 hours of discharge) or the control group (standard-of-care). The randomization scheme utilized permuted block with two stratification factors, SES and state, to ensure equal allocation of the intervention within each stratification block. Random permutations within each block within each stratum were generated using a random number generator available in SAS Proc Plan. The planned enrollment is a total of 900 patients with enrollment ending October 31, 2016.
- **1.1 Study Objective**: To evaluate the effectiveness of a nurse-led telephone intervention for families following their child's hospitalization for acute illness.

Working hypothesis 1: Patients who receive the nurse phone call will have a significantly lower occurrence of any unplanned re-hospitalization and/or any emergency/urgent care visits within 30 days of hospital discharge compared to the patients enrolled in the standard-of-care group.

Working hypothesis 2: Patients who receive the nurse phone call will have significantly better post discharge coping difficulty scores and faster return to normalcy compared to patients in the standard-of-care group.

1.2 Outcome measures

Primary

- Unplanned re-hospitalization and/or any emergency/urgent care visits within 30 days of hospital discharge.
 - o Dichotomized as any event reported through CCHMC or the HIE HealthBridge
 - Unplanned CCHMC hospital admissions will be defined as <=24 hour difference between scheduled entry and admission time for CCHMC events with this time data available
 - Non-CCHMC hospital admissions and outpatient visits will be classified as unplanned or planned by study team review of attending physician name in the data received from HealthBridge
 - o Non-CCHMC outpatient visits will be classified as urgent care by study team review of attending physician name in the data received from HealthBridge
 - All ED visits will be classified as unplanned
 - o CCHMC and non-CCHMC HealthBridge urgent care visits will be classified as unplanned

Secondary

- Post-Discharge Coping Difficulty Scale (PDCDS) total score
- Days back to normal routine perceived by caregiver (number of days 0 to >=14 days)
- Type specific, hospital and ED admissions only, within 30 days of hospital discharge.
 (dichotomized as any hospital/ED reported event through the HIE or CCHMC EPIC)
- Early re-utilization within 14-day post-discharge (HIE data or CCHMC Epic or parent report)

1.3 Subgroup analysis measures

- Financial strain subgroups as high strain vs. low/moderate strain
- · Access to primary care subgroups as high vs. moderate vs. low access
- Caregiver education as high school graduate vs. no high school degree
- Insurance (Public vs. all others)

1.4 Schedule of visits

- Pre-discharge in person interview (baseline)
- Nurse phone call within 96 hours of discharge from index event for the intervention group only
- 14-day post-discharge interview phone call (14-day follow-up)

1.5 Data Management

CCHMC DMC staff will guide data management for this project. Please see data management plan in the appendix.

1.6 Interim Safety Analyses

No interim analyses are planned for this study.

1.7 Exploratory Analysis

Following the completion of both the parent and supplement studies' planned analyses, we will conduct a secondary analysis to estimate outcome differences among the 4 arms (parent study-nurse visit, parent study-control, supplement study-phone call, and supplement study-control) if requested by the funding agency.

2. Statistical Reports

2.1 Report Generation

2.1.1 Deviations from Statistical Plan

The final statistical reports will describe and justify any deviations from the original statistical plan described herein.

2.1.2 Software

The statistical reports will be prepared using SAS 9.3 and R 3.2 under Microsoft Windows operating system.

2.2 Analysis Populations

2.2.1 Screen Failures

Patients screened using EPIC data, randomly selected to be approached for participation, and did not give written consent are considered screen failures. Patients who give informed written consent but are

not randomized are considered screen failures. Screen failures will be categorized as eligible but refused or eligible but not randomized (all eligible but not randomized for any reason except refused). The study coordinators will provide to the data management in excel format reasons for screen failure (categorized), age, census tract poverty (high vs. low), and state of residence (Ohio vs. Kentucky) for screen failed patients. These characteristics will be summarized using counts and percentage for categorical variables and mean, median, variance, range for age for all screened failed patients. Note that this summary will be at the admission level, such that a patient can be included more than once for multiple admissions.

2.2.2 Intent-to-Treat (ITT) Population

An ITT population will be defined as all patients who are randomized to a trial arm. For all practical purposes, it is expected that these patients will satisfy the minimum requirements for inclusion in the outcome analyses. The distinction between strict ITT patient and the ITT analysis group is made a priori to cover a situation in which a patient is randomized and, for whatever reason, the informed consent is invalid or withdrawn by the patient/family.

2.2.3 Intent-to-Treat Analysis (ITT-A) population

ITT patients with invalid/withdrawn consent will not be included in the statistical analyses, as we will not be able to collect/store any data from patients with invalid/withdrawn consent.

2.2.4 Per-Protocol Analysis (PPA) population

Patients in the ITT-A population who have no major protocol deviations/violations, as determined by the H2O study PIs, will be included in the PPA presentation and analyses. PPA will be defined by intervention adherence (received the nurse phone call within 96 hours for those in the home visit arm, did not receive a traditional home visit for those in the control arm within 96 hours), and completed (or partially completed) the 14 day follow-up survey within 14+9 days of index discharge date.

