2.3.1 Description of study population

Sample size:

The total number of patients who are screened, consented, randomized, and withdrawn will be given. A summary of patients with protocol violations, such as failed nurse phone call, or who were withdrawn will be provided.

Demographics and Clinical Characteristics, Patient and Parent:

Demographic and clinical characteristics as measured at baseline will be summarized by trial arm. Variables to be summarized are: child age, only child indicator, first hospitalization indicator, parent or caregiver age, race/ethnicity, education, marital status, household income, employment status, primary payor, financial strain, access to primary care, census track poverty (high vs. low percentage below poverty), state of residence (Ohio vs. Kentucky). Primary discharge diagnosis ICD9 or ICD10 codes will be categorized using the AHRQ CCS algorithm. Variables will be summarized using descriptive statistics appropriate for each type of data item.

Baseline characteristics with large differences between groups will be included in analyses evaluating the effectiveness of the intervention.

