2.3.2 Primary outcome analysis

Primary outcome: unplanned re-hospitalization and/or any emergency/urgent care visits within 30 days of hospital discharge

For the primary outcome, the dependent variable will be a dichotomized indicator of any occurrence of unplanned re-hospitalization and/or any emergency/urgent care visits within 30 days of hospital discharge recorded in CCHMC Epic or Healthbridge for non-CCHMC events. Differences between intervention and control groups on this outcome will be evaluated using logistic regression with the stratification variables (census tract poverty and state of residence). Other potential covariates (e.g. baseline characteristics of age, first hospitalization, only child, caregiver education, with large differences between groups) will be included in a secondary analysis model evaluating the effectiveness of the intervention.

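### The Aim 4 per-protocol rule may remove children with early returns from the phone arm but not from the control arm, a bias component of unknown size that favours the call

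*SAP*

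**What the plan says.** SAP 2.2.4 sets three adherence conditions for the per-protocol population, which is drawn from patients without major deviations as judged by the study PIs:

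- Intervention arm: "PPA will be defined by intervention adherence (received the nurse phone call within 96 hours for those in the home visit arm". Aim 4 has no home visit arm, so this can only mean the phone arm.
- Control arm: "did not receive a traditional home visit for those in the control arm within 96 hours".
- Both arms: "completed (or partially completed) the 14 day follow-up survey within 14+9 days of index discharge date".

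SAP 1.4 schedules the contact for one arm: "Nurse phone call within 96 hours of discharge from index event for the intervention group only". The primary outcome in SAP 1.2 is "Unplanned re-hospitalization and/or any emergency/urgent care visits within 30 days of hospital discharge", and SAP 2.3.2 analyses "any occurrence of unplanned re-hospitalization and/or any emergency/urgent care visits within 30 days of hospital discharge recorded in CCHMC Epic or Healthbridge". The clock therefore starts at discharge. SAP 1.2 also lists early re-utilization within 14 days of discharge as a secondary outcome.

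SAP 2.3.1 promises "A summary of patients with protocol violations, such as failed nurse phone call", and SAP 2.2.8 gives not completing the intervention inside its window as an example of a reason for exclusion. SAP 2.3 says that randomized patients are analysed in the arm to which they were allocated. The SAP does not say which outcomes the per-protocol analysis covers.

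**The concern.** In the phone arm, membership of the per-protocol population is settled by something that happens up to 96 hours after discharge, and those 96 hours already count towards the outcome. Suppose a child is readmitted on day 1 and so is not called in time. In the phone arm that child is non-adherent and leaves the analysis, taking the event along. In the control arm there is no call to miss, so the same event is not a ground for removal. This is immortal time in one arm. The control condition on home visits is not a counterpart, because it does not require the child to be at home, reachable or event-free for 96 hours.

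At stake is how the supportive analysis is read. Readers often take a per-protocol result as the effect of actually receiving the call, and this rule can produce fewer events in the phone arm when the call does nothing.

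**Working it through.** **The plan's own figure.** The protocol (Data Analysis/Methods, Aim 4, sample size) claims 80% power for 20% against 12.9% with 750 controls and 450 phone patients, alpha 0.05 and 11% noncompliance. I take the test as two-sided, which is stated only for the secondary outcomes, and noncompliance as dilution.

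- Diluted phone rate: 0.20 − 0.89 × 0.071 = 0.1368, a difference of 0.0632.
- Standard error under the null (pooled rate 0.1763): √[0.1763 × 0.8237 × (1/750 + 1/450)] = 0.0227.
- Standard error under the alternative: √[0.16/750 + 0.1368 × 0.8632/450] = 0.0218.
- Power: Φ[(0.0632 − 1.96 × 0.0227)/0.0218] = Φ(0.855) = 0.804.

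The figure reproduces, so 20% and 7.1 points serve as benchmarks below.

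**Inputs for the bias.** The control rate is 0.20, from the protocol. Two quantities are not in the documents and are assumed:

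- f: among children with an event by day 30, the share whose first event falls in the first 96 hours. Even timing gives 4/30 = 13.3%; 25% stands for front-loaded events.
- g: the share of those early events that both precede the call and prevent it by 96 hours. If events and calls are spread evenly over 96 hours, about half of early events precede the call. Then g = 50% needs every one of these to block the call, and g = 25% needs half of them to. g = 100% needs every early event to do both.

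**Formula, assuming the call has no effect.** A fraction 0.20fg of the phone arm, all with events, is removed:

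- Phone-arm per-protocol rate = 0.20(1 − fg)/(1 − 0.20fg); the control rate stays 0.20.
- The remaining non-events are 0.80/(1 − 0.20fg), so the spurious odds ratio is 1 − fg.

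The last column is Φ(difference/SE − 1.96), with 450 controls (900 randomized 1:1, SAP 1) and 450(1 − 0.20fg) phone patients. Its nominal value is 2.5%. Survey losses and other missed calls are ignored.

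| f | g | fg | Phone rate | Drop (points) | OR | Falsely significant in favour of the call |
|---|---|---|---|---|---|---|
| 13.3% | 25% | 0.033 | 0.1933/0.9933 = 19.5% | 0.5 | 0.97 | 3.9% |
| 13.3% | 50% | 0.067 | 0.1867/0.9867 = 18.9% | 1.1 | 0.93 | 6.0% |
| 25% | 50% | 0.125 | 0.175/0.975 = 17.9% | 2.1 | 0.875 | 11.9% |
| 25% | 100% | 0.25 | 0.15/0.95 = 15.8% | 4.2 | 0.75 | 37.1% |

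Against the 7.1-point design difference, the drops of 0.5, 2.1 and 4.2 points are 8%, 29% and 59%. For the 14-day outcome, even timing puts 4/14 = 29% of events in the first 96 hours, so the exposure there is greater.

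**Check of a common landmark.** If children with an event in the first 96 hours are left out of both arms, the null rate in each arm is 0.20(1 − f)/(1 − 0.20f). That is 17.8% in both arms at f = 13.3% and 15.8% in both at f = 25%. The spurious odds ratio returns to 1.

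**The case against.** The strongest reply is that the rule may seldom bite. The intervention is a telephone call, and the outcome includes any ED or urgent care visit. A child seen and sent home on day 1 can still be called within 96 hours, and nothing in the documents says that a return cancels the call. At f = 13.3% and g = 25% the shift is 0.5 points, against a standard error of √(2 × 0.16/450) = 2.7 points at 450 per arm. That stands, and it is why the size has to be left open.

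A reader might go further and infer that every child who returns before the call leaves the phone arm, so that the per-protocol result as a whole will make the call look protective. The documents support neither step. The first turns a possibility into a certainty. The second overlooks calls missed because families are unreachable or decline, which could move the contrast either way. Nor may one infer that the main result is affected: SAP 2.3 analyses patients as allocated. It is also an inference, though a natural one, that the per-protocol analysis will be run on utilization, since SAP 2.3.2 to 2.3.4 attach it to no outcome.

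The reply does not remove the asymmetry. No passage exempts a child who returned before the call, starts follow-up at 96 hours, or puts a matching condition on controls. PI judgement of major deviations does not settle it, because 2.2.4 goes on to define adherence explicitly.

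**Conclusion.** The point holds as a flaw in a supportive analysis. As written, SAP 2.2.4 can take early events out of the phone arm only, and this component of bias favours the call whenever any early return blocks a call.

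With no true effect and a 20% rate, a reasonable range for the spurious drop is 0.5 to 2.1 points, with 4.2 points as an extreme. These figures rest on assumed values of f and g and on the per-protocol population being used for utilization outcomes. The net direction of the per-protocol result is not established, and the as-allocated primary analysis is untouched. The change is worth making because it is cheap.

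**What to change.** Add to SAP 2.2.4, for any per-protocol analysis of the 30-day or 14-day utilization outcomes, a landmark applied alike in both arms:

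- Set it at 96 hours after discharge, or at day 4 where only dates exist. SAP 1.2 refers to CCHMC events with time data available, and the Data Management Plan does not show event times for every source.
- Include only children with no qualifying event by the landmark.
- Define adherence in each arm at that point.
- Count events from the landmark to the end of the outcome window.
- Label the analysis supportive, and state which outcomes it covers.

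In the same section, reconcile the reference to a home visit arm with the Aim 4 phone arm.

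The drafting cost is a few sentences. The analytic cost is larger: events before the landmark are not counted. On the assumptions above that is 13% to 25% of 30-day events, or about 12 to 23 of the 0.20 × 450 = 90 expected per arm, and a larger share for the 14-day outcome. Confounding from calls missed for other reasons remains.

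I would not instead keep phone-arm children whose event preceded the call while still dropping event-free children who missed it. With fg = 0.125 and 11% of the others missing the call, the null phone rate becomes (0.025 + 0.89 × 0.175)/(0.025 + 0.89 × 0.975) = 20.2%, a small bias in the opposite direction.

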2.2.7 Missing data

We will continue to collect EHR data (CCHMC Epic and HealthBridge) for the primary outcome for all study participants unless consent is withdrawn. Our approach for handling missing data will be to first assess consent withdrawal rates and evaluate whether or not the rates are very different between the two arms of the trial. If the rates/reasons are similar, we will perform the analysis assuming *Missing Completely at Random (MCAR)*, i.e., the propensity for a data point to be missing is completely random such that there is no relationship between whether a data point is missing and any values in the data

set, missing or observed (missing data are a random subset of the data). If consent withdrawal rates are very different between the two arms of a trial, then our results will be limited by concerns about potential bias. For secondary outcomes of post-discharge coping difficulty and days back to normal subject-reported outcomes collected at the 14-day phone call, missing outcome data could occur for several reasons, such as item nonresponse, lost to follow-up, and data collection errors. Our approach for handling missing secondary outcome data will be to first assess missing patterns/reasons for missing, understand the distribution of missing data, and evaluate any differences between the two trial arms. This will allow us to assess whether an assumption of MCAR (missing data are a random subset of the data) is reasonable or if missingness is conditional on another variable in the dataset, i.e., Missing at Random (MAR). We will use descriptive statistics to compare baseline characteristics of patients with and without missing data. If MAR, we will incorporate variables that are identified to be related to the missingness in the analysis using multiple imputation, as multiple imputation works best when good predictors of outcome are available.

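### The single Aim 4 per-protocol population applies a survey condition that the records-based outcomes do not need, and its control-arm rule does not list receipt of the study call

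*SAP*

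**What the plan says.** SAP 2.2.4 builds the per-protocol (PPA) population from ITT-A patients who meet three conditions:

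- They have "no major protocol deviations/violations, as determined by the H2O study PIs".
- They adhered to allocation. In the intervention arm this means "received the nurse phone call within 96 hours for those in the home visit arm"; in the control arm it means "did not receive a traditional home visit for those in the control arm within 96 hours".
- They "completed (or partially completed) the 14 day follow-up survey within 14+9 days of index discharge date".

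The third condition matches SAP 2.2.5, which counts a patient as having completed the study once the 14-day interview is done, with the same nine-day allowance.

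The outcomes draw on different sources. SAP 2.3.2 takes the primary outcome from events "within 30 days of hospital discharge recorded in CCHMC Epic or Healthbridge for non-CCHMC events", and SAP 2.2.7 adds: "We will continue to collect EHR data (CCHMC Epic and HealthBridge) for the primary outcome for all study participants unless consent is withdrawn". The 30-day hospital/ED outcome in SAP 1.2 uses the same records. The coping scale (PDCDS) and days back to normal come from the 14-day interview. One further secondary outcome mixes sources: "Early re-utilization within 14-day post-discharge (HIE data or CCHMC Epic or parent report)".

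The Aim 4 intervention, in SAP section 1, is "a nurse phone call within 96 hours of discharge". SAP 2.3 never mentions the PPA. It says that randomised patients are analysed as allocated.

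**The concern.** A survey condition makes sense for an outcome measured by the survey. For an outcome read from hospital records it only removes children whose result is known. The interview can fall anywhere from day 14 to day 23 and still count, which is inside the 30-day window of the primary outcome. A revisit in the first weeks could make a family easier or harder to reach, so the condition may select on the outcome, and differently by arm. Interviews on days 24 to 30, which the protocol's Follow-up Questionnaire text permits, also fail the PPA rule.

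The control-arm rule has a gap of its own. The direct form of contamination in this trial is a control child who receives the study nurse call, and that is not listed. Such a child leaves the PPA only through the general clause on major deviations, which is a judgement by the PIs.

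At stake is how clean the supportive analysis is. The main analysis is not affected.

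**Working it through.** **The plan's own figure.** The protocol's Aim 4 sample-size text gives 750 control and 450 phone, 20% against 12.9%, alpha 0.05, 11% noncompliance, 80% power. I took the test as two-sided, which the text states for the secondary outcomes.

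- Diluted phone rate: 0.89 × 0.129 + 0.11 × 0.20 = 0.1368.
- Pooled-variance power for 0.20 against 0.1368: 80.4%, which agrees with the stated 80%.

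The 11% is thus reproduced with noncompliers kept in their arm. It is an allowance for the main comparison, not the plan for a PPA. The 5% attrition appears only for the secondary survey outcomes.

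**Inputs for the PPA.**

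- Control rate 0.20 (protocol, Aim 4 sample size), used in both arms.
- 11% of the phone arm removed by the call rule. Reading the protocol's noncompliance as children not called in time is my assumption.
- Survey loss m = 5% (protocol, Aim 4 secondary outcomes), taken as equal in both arms and unrelated to receipt of the call.
- Size: 900 at 1:1 (SAP section 1), or 750 + 450 (protocol). The two documents disagree, so both are shown.

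**Formula.** With a phone and b control children retained, the half-width is 1.96 × √(0.16/a + 0.16/b).

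*SAP size, 450 per arm.*

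- Call rule only: a = 450 × 0.89 = 400.5, b = 450, total 850.5. Half-width 5.39 points.
- Survey rule added: loss 0.05 × 850.5 = 42.5, leaving 808.0. Half-width 5.39/√0.95 = 5.53.
- Assumed m of 10% or 15%: 765.5 or 722.9 kept, half-width 5.68 or 5.84.

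*Protocol size, 750 + 450.*

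- Call rule only: a = 400.5, b = 750, total 1150.5. Half-width 4.85 points.
- Survey rule added: loss 0.05 × 1150.5 = 57.5. Half-width 4.85/√0.95 = 4.98.

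Interviews on days 24 to 30 would add to these losses. Their number is not given.

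**Selection.** Take no true effect and a rate of 0.20 in each arm. If non-responders have event rate r, the retained rate is (0.20 − m × r)/(1 − m).

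- Equal loss and the same r in both arms: difference 0.
- m = 5%, r = 0.20 in one arm and 0.30 in the other: 0.2000 against 0.1947, or 0.53 points.
- m = 5%, r = 0.10 against 0.30: 0.2053 against 0.1947, or 1.05 points.
- Loss of 7% against 3%, r = 0.10 or 0.30 in both arms: 0.44 points, with opposite signs.

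Only the 5% comes from the documents. The values of r and the unequal losses are illustrations, and the sign changes with which arm or which r is chosen.

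**Control-arm rule.** No arithmetic applies. The intervention is a nurse phone call; the listed control deviation is a traditional home visit. No sentence in 2.2.4 lists the study call.

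**The case against.** The strongest defence is that the survey rule is deliberate. Its window is that of the completion definition in SAP 2.2.5, so the PPA is a population of adherent completers, used for everything. That is a recognised and internally consistent construction, and having one population is simple to report. This stands as an explanation of the rule. It does not supply a benefit for outcomes that need no interview.

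Four stronger readings are tempting, and the documents do not support them.

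- A reader might infer that the primary outcome will lose these children. The SAP names no outcome for the PPA, so the loss arises only if the PPA is run on a records-based outcome. Nothing in 2.2.4 prevents that.
- A reader might infer a contradiction with the sample-size plan, because the primary outcome was planned without attrition. Those allowances belong to the main comparison; no PPA was powered.
- A reader might treat the exclusion of uncalled phone-arm children as a further fault, since an early revisit could prevent the call. That is a general limit of per-protocol analysis, and its size here cannot be derived from the documents.
- A reader might take the reference to a home visit arm to mean that the wrong arm is analysed. The intended arm is plain, so this is a clerical slip.

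On called controls, SAP 2.2.8 requires the reason for an exclusion and who decided it, and SAP 2.3.1 requires a summary of protocol violations. An exclusion by the PIs would therefore be documented. It would still not be prespecified. The protocol's silence on a per-protocol analysis for Aim 4 is no error, since the SAP supplies one.

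**Conclusion.** The point holds in a limited form. If the PPA is applied to the primary or the 30-day hospital/ED outcome, the survey condition removes children whose outcome is available from records, selects on a post-randomisation event within the outcome window, and gains nothing for those outcomes. At 5% loss the cost is about 0.14 points of half-width on the SAP's size (5.53 − 5.39) and 0.13 on the protocol's (4.98 − 4.85). Bias is zero if losses and non-responder event rates are the same in both arms. Otherwise its direction and size are unknown, and no claim that it favours either arm is supported. The unlisted study call to a control is a genuine gap in the rule, now left to judgement. The arm label is a wording error, and the unnamed PPA outcomes are missing detail.

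The ITT-A conclusion does not depend on any of this. Severity: minor. Confidence is high on the text and lower on any bias, which rests wholly on assumed rates.

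**What to change.** In SAP 2.2.4:

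- Apply the survey condition only to PDCDS, days back to normal, and the 14-day early re-utilization outcome. Apply it to that last outcome as a whole: it is a single composite that includes parent report, and keeping non-responders in would leave that component unobserved. Do not apply it to the primary or the 30-day hospital/ED outcome.
- List receipt of the study nurse phone call as a control-arm deviation beside the home-visit rule.
- Correct the label of the intervention arm to the nurse phone call arm.

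In SAP 2.3, state for which outcomes PPA results are produced and that they support the ITT-A analysis.

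The cost is a few sentences. No new data are needed, and the records-based PPA regains the children lost to the survey rule.
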